4.1, 4.3	Study background and summary of nonclinical data is revised.	To more fully describe the study background and nonclinical data as presented in the IB.
4.4	Clinical experience from the recently completed EVO756-HV001 clinical study is updated.	To reflect the most current clinical experience with EVO756 in alignment with the revised IB and describe the rationale for the selected dose.
██████████ ████	████████████████████ ████████████████████ ██████████	████████████████████ ████████████████
██████████ ████	████████████████████ ████████████████████	████████████████████ ████████████████████
██████████	████████████████████ ████████████████████	████████████████████ ████████████████████ ████████████████████ ████████████████████ ████████████████████ ████████████████████ ████████████████████
8.2.6	Clarification added that on Day 1, blood samples will be collected prior to study drug administration.	To provide guidance on timing of baseline blood sample collection relative to the first dose.
10.4	Additional detail regarding study drug administration. Additional information to sites and subjects on recording missed doses and the timing of their last dose prior to the Week 1, 2, and 4 provocation tests on a form are added.	Added clarification on dosing instructions.
11.2.3	The statement “If no valid reason exists for suggesting a relationship, then the AE should be classified as ‘not related’...” is removed.	To clarify the requirements for assessing relatedness of AEs to study drug.
██████████	████████████████████ ████████████████████	████████████████████ ████████████████████
Table 4	The Week 4 visit window is changed to -3 days.	The previous window of ± 3 days was an oversight. Because provocation testing is conducted at Week 4, the visit cannot occur after treatment completion.

SPONSOR SIGNATURE PAGE**AN OPEN LABEL STUDY EVALUATING THE SAFETY, TOLERABILITY, AND EFFICACY OF EVO756 IN ADULTS WITH CHRONIC INDUCIBLE URTICARIA****Protocol Number: EVO756-CIU001****Protocol Final Date: 31May2024****Protocol Amendment 1: 23Jul2024****Protocol Amendment 2: 03Sep2024****Protocol Amendment 3: 10Jan2025**

- AST, ALT, alkaline phosphatase, or total bilirubin above the ULN at Screening.
- History of hypersensitivity to EVO756, its components, or drugs of similar classes.
- Participation in a clinical research study involving the administration of an investigational or marketed drug or device within 30 days (or 5 half-lives, whichever is longer) or within 120 days (or 5 half-lives, whichever is longer) for investigational biologics prior to Day 1, or concomitant participation in an investigational study involving no drug or device administration. Participation in non-interventional registries or epidemiological studies is allowed.
- Concomitant use of the following medications for the timeframes specified below and while on study:
 - Biologics (e.g., omalizumab, dupilumab, tezepelumab, ligelizumab) for 120 days or 5 half-lives (whichever is longer) prior to Day 1,
 - Cyclosporine, methotrexate, sulfonamides, systemic glucocorticoids (e.g., prednisone), or mycophenolate mofetil for 28 days prior to Day 1,
 - A live or live-attenuated vaccine for 14 days prior to Day 1,
 - Leukotriene inhibitors (e.g., montelukast, zafirlukast) for 14 days prior to Day 1 (if being used to treat CIndU or CSU),
 - H₂-receptor antagonists [e.g., ranitidine, famotidine]) for 14 days prior to Day 1 (if being used to treat CIndU or CSU),
 - Long-acting antihistamines (e.g. H₁-receptor antagonists such as, loratadine, desloratadine, fexofenadine, cetirizine, and levocetirizine) for 7 days prior to the first provocation test during the screening period,
 - Short-acting antihistamines (e.g., H₁-receptor antagonists such as hydroxyzine, diphenhydramine) for 3 days prior to the first provocation test during the screening period.
- History of diseases other than CIndU or Chronic Spontaneous Urticaria (CSU) with urticaria or angioedema symptoms, such as urticarial vasculitis, erythema multiforme, cutaneous mastocytosis (urticaria pigmentosa), and hereditary or acquired angioedema.
- Any other skin disease or skin markings (e.g., extensive scarring, tattoos) that might confound the assessment of CIndU provocation or pruritus evaluation in the Investigator's opinion.
- Significant medical history, other than CIndU, or sequelae of gastrointestinal (e.g., peptic ulcer, gastrointestinal bleeding), liver or kidney disease, uncontrolled cardiovascular disease, or any other condition which might interfere with the evaluation of safety or provocation of CIndU.

Criteria for evaluation:Safety:

Safety will be assessed through an evaluation of treatment emergent adverse events (TEAEs), physical exams, vital signs, laboratory tests (serum chemistry, hematology, and urinalysis), and 12-lead ECGs.

Efficacy:

Efficacy of EVO756 in reducing wheal formation following standardized provocation will be assessed:

- In subjects with cold induced urticaria, the TempTest will be used to induce wheals and the Critical Temperature Threshold will be measured. The CTT determines the highest temperature sufficient for inducing symptoms.
- In subjects with symptomatic dermatographism, the FricTest will be used to induce wheals and the Total Fric Score (TFS) will be measured. The TFS represents the number of wheals induced following the test, from 0 to 4.
- Efficacy of EVO756 in reducing the severity of pruritus at the provocation test site

Statistical methods:Sample size justification:

The sample size of this study is based on clinical considerations only.

Analyses for primary and secondary objectives:Safety and tolerability:

Descriptive summary statistics will be prepared and reported for TEAEs. Changes from baseline will be summarized for vital signs, 12-lead ECG, and clinical laboratory parameters.

Efficacy:

In subjects with cold urticaria, mean absolute change from baseline in CTT and proportion of subjects who are complete responders will be calculated at Weeks 1, 2, and 4.

In subjects with symptomatic dermatographism, mean absolute change from baseline in TFS and proportion of subjects who are complete responders will be calculated at Weeks 1, 2, and 4.

Worst pruritus-NRS score at the provocation test site will be assessed.

Additional details will be described in the Statistical Analysis Plan (SAP).

3. LIST OF ABBREVIATIONS AND DEFINITIONS OF TERMS

The following abbreviations and specialist terms are used in this study protocol.

Table 2: Abbreviations and Specialist Terms

Abbreviation or Specialist Term	Explanation
AE	Adverse event
BID	Twice daily
CIndU	Chronic inducible urticaria
CSU	Chronic Spontaneous Urticaria
CTT	Critical Threshold Temperature
████	████████████████
GCP	Good Clinical Practice
EOT	End of Treatment
IB	Investigator's Brochure
IC90	90% inhibition concentration
ICH	International Conference on Harmonization
IEC	Independent Ethics Committee
████	████████████████
████	████████████████
████	████████████
████	████████████
████	████████████
IRB	Institutional Review Board
MC	Mast cells
MRGPRX2	Mas-related G-protein coupled receptor member X2
NRS	Numeric Rating Scale
OAE	Other significant adverse event
OTC	Over the counter
PI	Principal Investigator The investigator who leads the study conduct at an individual study center. Every study center has a principal investigator.
QD	Once daily
SAE	Serious adverse event
TFS	Total Fric Score
████	████████████████████████████

4.1. [REDACTED]

[REDACTED]

[illegible]

[REDACTED]

[REDACTED]

[REDACTED]

[REDACTED]

[REDACTED]

[REDACTED]

[REDACTED]

[REDACTED]

[REDACTED]

[REDACTED]

[REDACTED]

[REDACTED]

[REDACTED]

[REDACTED]

[REDACTED]

[REDACTED]

[REDACTED]

[REDACTED]

[REDACTED]

[REDACTED]

[REDACTED]

[REDACTED]

[REDACTED]

[REDACTED]

[REDACTED]

[REDACTED]

[REDACTED]

[REDACTED]

[REDACTED]

[REDACTED]

[REDACTED]

[REDACTED]

[REDACTED]

[REDACTED]

[REDACTED]

[REDACTED]

[REDACTED]

[REDACTED]

[REDACTED]

[REDACTED]

[REDACTED]

[REDACTED]

5. TRIAL OBJECTIVES AND EFFICACY ENDPOINTS

5.1. Primary Objective

The primary objective of this study is to evaluate the safety and tolerability of EVO756 in subjects with CIndU.

5.2. Secondary Objectives

The secondary objectives of this study are:

- To assess the efficacy of EVO756 in reducing wheal formation following a standardized provocation test in CIndU (cold urticaria or symptomatic dermographism).
- To assess the efficacy of EVO756 in reducing pruritus at the site of the urticaria provocation tests.

[REDACTED]

5.4. Endpoints

5.4.1. Safety

Safety will be assessed through an evaluation of treatment emergent adverse events (TEAEs), physical exams, vital signs, laboratory tests (serum chemistry, hematology, and urinalysis), and 12-lead ECGs.

5.4.2. Efficacy

Efficacy of EVO756 in reducing wheal formation following standardized provocation will be assessed by:

- In subjects with cold urticaria, [REDACTED]
[REDACTED]
- In subjects with symptomatic dermographism, [REDACTED]
[REDACTED]
- Worst pruritus-NRS score at the provocation test site [REDACTED]
[REDACTED]

[REDACTED]

6. INVESTIGATIONAL PLAN

6.1. Overall Study Design

This is a multi-center Phase 2a open label study evaluating the safety, tolerability, and efficacy of EVO756 in approximately 30 adult subjects with CIndU. During screening, subjects will be evaluated for cold urticaria or symptomatic dermographism by the TempTest or the FricTest to determine baseline sensitivity to a cold or pressure provocation, respectively. [REDACTED]

[REDACTED] Subjects will be evaluated for IgE levels at Screening and will be identified as either an IgE low subject [REDACTED] or an IgE high subject [REDACTED]

Subjects will be seen on an outpatient basis at the study center at Screening, Day 1, Week 1, Week 2, Week 3, and Week 4 (End of Treatment). Subjects will return to the study center for a Study Exit visit at Week 6.

Efficacy will be assessed using a TempTest for subjects with cold urticaria or FricTest for subjects with symptomatic dermographism, and [REDACTED] pruritus-NRS at the site of the urticaria provocation test for all subjects.

Safety will be assessed through an evaluation of treatment emergent adverse events (TEAEs), physical exams, vital signs, laboratory tests (serum chemistry, hematology, and urinalysis), and 12-lead ECGs.

[figure not shown]
6.2. Number of Subjects

Approximately 30 subjects with CIndU will be enrolled in this study.

6.3. Duration of the Study

The duration of participation for each subject is expected to be approximately 10 weeks (up to 30 days for screening, 4 weeks of treatment, and 2 weeks of follow-up).

See [Figure 1](#) for a schema of the study design.

Figure 1: Study Design

7. STUDY POPULATION

7.1. Subject Inclusion Criteria

1. Male or female aged ≥ 18 to ≤ 65 years, at the time of consent.
2. BMI > 18.0 and ≤ 35.0 kg/m² at Screening.
3. Capable of providing informed consent and willing and able to comply with study requirements. Note: consent must be obtained prior to any study-related procedures.
4. Confirmed CIndU diagnosis with either cold urticaria or symptomatic dermographism for ≥ 3 months.
5. Positive provocation test result at Screening and Day 1 visits (see Section 8.2.6.5)
 - a. For subjects with cold urticaria, wheal formation at temperatures ≥ 16 °C using the TempTest.
 - b. For subjects with symptomatic dermographism, TFS of ≥ 2 using the FricTest.
6. WOCBP (childbearing potential females are defined as women that are neither postmenopausal nor surgically sterile) who are sexually active with a non-sterile male partner (sterile male partners are defined as men vasectomized since at least 6 months prior to screening) must be willing to use highly effective contraceptive methods at least 28 days prior to Day 1 and throughout the study and for 90 days after the last study drug administration.
 - a. The following are highly effective contraceptive methods: combined (estrogen and progestogen containing) hormonal contraception (oral, intravaginal, transdermal, injectable, implantable) associated with inhibition of ovulation, progestogen-only hormonal contraception (oral, injectable, implantable) associated with inhibition of ovulation, intrauterine device (IUD), intrauterine hormone-releasing system (IUS), bilateral tubal occlusion, vasectomized partner, or sexual abstinence. The reliability of sexual abstinence should be evaluated in relation to the duration of the clinical trial and the preferred and usual lifestyle of the subject. Periodic abstinence (e.g., calendar, ovulation, symptothermal, or post-ovulation methods) and withdrawal are not acceptable methods of contraception.
 - b. Female subjects who are not WOCBP must be either post-menopausal (at least 12 months of amenorrhea in the absence of other biological causes with a documented serum FSH confirming nonchildbearing potential as per laboratory ranges confirmatory levels at Screening) or surgically sterilized (hysterectomy, bilateral oophorectomy, and/or bilateral salpingectomy).
7. Male subjects who are not vasectomized for at least 6 months prior to screening, and who are sexually active with a WOCBP must be willing to use an effective barrier method of contraception from the first study drug administration until at least 90 days after the last study drug administration. Female partners of male subjects who are WOCBP should use acceptable contraceptive methods at least 28 days prior to Day 1, throughout the study, and for 90 days after the last study drug administration.

8. Male subjects must not donate sperm from the first study drug administration until 90 days following the last study drug administration.
9. Female subjects must not donate oocytes or undergo in vitro fertilization from the first study drug administration until 90 days following the last study drug administration.

7.2. Subject Exclusion Criteria

1. Any clinically significant abnormality in laboratory evaluations, physical examinations, vital signs, or ECG at Screening, in the opinion of the Investigator.
2. Known history of HIV, hepatitis B, or hepatitis C.
3. AST, ALT, alkaline phosphatase, or total bilirubin above the ULN at Screening.
4. History of renal disease, creatinine level 1.25x above ULN, or creatinine clearance <60 ml/min (using the Cockcroft-Gault or CKD-EPI equation) at Screening.
5. History of hypersensitivity to EVO756, its components, or drugs of similar classes.
6. History of clinically significant drug or alcohol abuse in the last year prior to Day 1.
7. Positive pregnancy test or breastfeeding at Screening and Day 1.
8. Women planning a pregnancy within the study period.
9. History of a major surgery within 8 weeks prior to Day 1, or major surgery planned during the study.
10. Participation in a clinical research study involving the administration of an investigational or marketed drug or device within 30 days (or 5 half-lives, whichever is longer) or within 120 days (or 5 half-lives, whichever is longer) for investigational biologics prior to Day 1, or concomitant participation in an investigational study involving no drug or device administration. Participation in non-interventional registries or epidemiological studies is allowed.
11. Concomitant use of the following medications for the timeframes specified below and while on study:
 - a. Biologics (e.g., omalizumab, dupilumab, tezepelumab, ligelizumab) 120 days or 5 half-lives (whichever is longer) prior to Day 1,
 - b. Cyclosporine, methotrexate, sulfonamides, systemic glucocorticoids (e.g., prednisone), or mycophenolate mofetil 28 days prior to Day 1,
 - c. A live or live-attenuated vaccine 14 days prior to Day 1,
 - d. Leukotriene inhibitors (e.g., montelukast, zafirlukast) 14 days prior to Day 1 (if being used to treat CIndU or CSU),
 - e. H2-receptor antagonists [e.g., ranitidine, famotidine]) 14 days prior to Day 1 (if being used to treat CIndU or CSU),
 - f. Long-acting antihistamines (e.g. H1-receptor antagonists such as, loratadine, desloratadine, fexofenadine, cetirizine, and levocetirizine) 7 days prior the first provocation test during the screening period,

- g. Short-acting antihistamines (e.g., H1-receptor antagonists such as hydroxyzine, diphenhydramine) for 3 days prior to the first provocation test during the screening period.
- 12. History of diseases other than CIndU or CSU with urticaria or angioedema symptoms, such as urticarial vasculitis, erythema multiforme, cutaneous mastocytosis (urticaria pigmentosa), and hereditary or acquired angioedema.
- 13. Any other skin disease or skin markings (e.g., extensive scarring, tattoos) that might confound the assessment of CIndU provocation or pruritus evaluation in the Investigator's opinion.
- 14. History of malignancy of any organ system (other than fully treated localized basal cell carcinoma or squamous cell of the skin or in situ cervical cancer), treated or untreated, within the past 5 years, regardless of whether there is evidence of local recurrence or metastases.
- 15. Significant medical history, other than CIndU, or sequelae of gastrointestinal (e.g., peptic ulcer, gastrointestinal bleeding), liver or kidney disease, uncontrolled cardiovascular disease, or any other condition which might interfere with the evaluation of safety or provocation of CIndU.
- 16. Any reason which, in the opinion of the Investigator, would prevent the subject from participating in the study or being compliant with study procedures.

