8.2.6. Laboratory Assessments

Laboratory tests will be collected as stipulated in the Schedule of Assessments, [REDACTED] will be analyzed at a central laboratory. Day 1 samples will be collected prior to study drug administration. Laboratory assessments may be repeated once during screening to qualify a subject for the study. All laboratory assessments, for screening and during the trial conduct, must be collected using the central laboratory. Sample handling, processing, and shipping information will be detailed in the Laboratory Manual.

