11.2.2. Reporting of Adverse Events

AEs spontaneously reported by the subject and/or in response to an open question from the study personnel or revealed by observation will be recorded during the study at the study center.

AEs should be recorded on the eCRF from the time the subject has signed informed consent through the last study visit. Any changes in the subject's status between signing informed consent, up to the time administration of the first dose of study drug will be recorded as a pre-treatment AE. Any AE occurring after administration of the first dose of study drug will be considered a treatment emergent AE (TEAE).

The AE term should be reported in standard medical terminology when possible.

Any subject who has an AE (whether serious or non-serious) or clinically significant test value will be evaluated by the Investigator or designee and will be treated and/or followed up until the symptoms or values return to normal or to clinically acceptable levels, or stabilize, as judged by the Investigator.

Unless a diagnosis is available, signs and symptoms must be reported as individual AEs in the eCRF; a diagnosis is preferred.

For each AE, the investigator will evaluate and report the onset date, resolution or stabilization date, intensity, causality, action taken, serious outcome (if applicable), and whether or not it caused the subject to discontinue the study.

Intensity will be assessed according to the National Cancer Institute (NCI) Common Terminology Criteria for Adverse Events (CTCAE), Version 5.0, 2017. The NCI Common Terminology Criteria for Adverse Events is a descriptive terminology which can be utilized for AE reporting. A grading (severity) scale is provided for each AE term. Grade refers to the severity of the AE. The CTCAE displays Grades 1 through 5 with unique clinical descriptions of severity for each AE based on this general guideline:

- Grade 1 – Mild; asymptomatic or mild symptoms; clinical or diagnostic observations only; intervention not indicated.
- Grade 2 – Moderate; minimal, local or noninvasive intervention indicated; limiting age-appropriate instrumental activities of daily living (ADL).

- Grade 3 – Severe or medically significant but not immediately life-threatening; hospitalization or prolongation of hospitalization indicated; disabling; limiting self-care ADL.
- Grade 4 – Life-threatening consequences; urgent intervention indicated.
- Grade 5 – Death related to AE.

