13.4.1. Other Safety Data

Laboratory test results will be summarized descriptively by visit. Additionally, shifts by study visit to Week 4 in laboratory test results based on normal ranges will be summarized with descriptive statistics. Individual laboratory test results will be presented in a by-subject listing. Any clinically significant laboratory abnormalities will be captured as AEs.

Vital signs will be presented as observed values and changes from Day 1 using descriptive statistics.

Medical histories will be coded using the MedDRA dictionary and presented in a by-subject listing.

Concomitant medications will be coded using the WHO-Drug dictionary. Concomitant medications will be summarized by drug class and preferred term.

Physical examination data will be presented in a by-subject listing.

Descriptive statistics by visit will be provided for the following ECG parameters: heart rate (HR), RR duration, QRS duration, PR duration, QT duration and QTcF and QTcB duration.

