## **14.2 Clinical Laboratory**

Laboratory data will be presented in SI units.

Observed values and changes from baseline in chemistry, hematology, and quantitative urinalysis tests will be summarized using descriptive statistics. Frequencies and percentages will be presented for each category of qualitative urinalysis tests.

Shift tables from baseline to each post-baseline visit describing shifts to abnormality based on the central laboratory reference ranges (low, normal, high for chemistry, hematology, and quantitative urinalysis; normal, abnormal for qualitative urinalysis) will be provided. Only subjects with a baseline result and a result at the specified post-baseline visit will be considered.

Separate listings of all data for chemistry, hematology, urinalysis tests and pregnancy will be provided.

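### SAP 14.2 tabulates liver tests only as low, normal or high by visit, so no table counts subjects by size of elevation or shows aminotransferase and bilirubin raised together

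*Protocol*

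**What the plan says.** Laboratory tests are among the measures that serve the primary safety objective (Protocol 5.1 and 5.4.1; SAP 2).

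Protocol 7.2, exclusion 3, rules out "AST, ALT, alkaline phosphatase, or total bilirubin above the ULN at Screening". Protocol 8.2.6 adds that "Laboratory assessments may be repeated once during screening to qualify a subject for the study" and that "Day 1 samples will be collected prior to study drug administration". The exclusion refers to Screening only and does not mention the Day 1 sample.

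SAP 14.2 plans three kinds of chemistry output:
- Continuous summaries: "Observed values and changes from baseline in chemistry, hematology, and quantitative urinalysis tests will be summarized using descriptive statistics". Under SAP 7.4 these include the minimum and maximum.
- Shift tables from baseline to each later visit, with the levels "low, normal, high for chemistry, hematology, and quantitative urinalysis; normal, abnormal for qualitative urinalysis". Protocol 13.4.1 is equally coarse: "shifts by study visit to Week 4 in laboratory test results based on normal ranges will be summarized with descriptive statistics".
- A listing of all chemistry data.

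SAP 6.4 says which samples count. In by-visit summaries, a repeat, unscheduled or early-termination result is used only if the scheduled one is missing and the substitute falls in the visit window. In summaries not presented by visit, all samples count, and the worst post-baseline value is the SAP's own example. SAP 14.2 plans no such summary.

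For adverse events, Protocol 11.2.2 states: "Intensity will be assessed according to the National Cancer Institute (NCI) Common Terminology Criteria for Adverse Events (CTCAE), Version 5.0, 2017". No equivalent grading is planned for the laboratory values themselves.

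**The concern.** For a liver test, the questions a safety reader asks are how far it rose, in how many subjects, and whether aminotransferase and bilirubin rose together in one person. The shift table answers none of these. Its top level begins at ULN and has no upper subdivision. Each test is also tabulated separately, so two tests cannot be linked within a subject.

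The SAP 6.4 rule adds a second gap. An abnormal result is a common reason for a recheck, and the recheck may hold the peak. If the scheduled sample exists, that peak enters neither the shift table nor the by-visit maximum.

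At stake is how clearly the study can report on part of its primary objective. A statement about the liver would have to be assembled by hand from listings and adverse event reports.

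**Working it through.** The documents state no laboratory rate, variance or threshold to reproduce, and the sample size of about 30 rests on clinical considerations (Protocol synopsis). The calculations below are illustrations with assumed inputs.

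**1. What the shift cell hides and the other summaries show.** Assume 15 subjects in a dose group, ULN 40 U/L, and every baseline at 20 U/L. In case A one subject rises to 44 (44/40 = 1.1 x ULN). In case B one subject rises to 400 (400/40 = 10 x ULN). The other 14 stay at 20.

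| Output | Case A | Case B |
|---|---|---|
| Shift cell, normal to high | 1 | 1 |
| Maximum (U/L) | 44 | 400 |
| Largest change (U/L) | 24 | 380 |
| Mean change (U/L) | 24/15 = 1.6 | 380/15 = 25.3 |
| SD (U/L) | 6.20 | 98.12 |

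The shift table cannot tell the cases apart. The continuous summary can, but it gives one extreme per test per visit. It does not say how many subjects passed a given level, or whether the highest ALT and the highest bilirubin belong to the same subject.

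**2. Effect of the sample rule.** Suppose the scheduled value is 44 and an unscheduled recheck reads 400. Under SAP 6.4 the by-visit tables use 44, so they report case A. The 400 appears in the listing, and as an adverse event only if the investigator judges that it qualifies.

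**3. Chance counts.** A simulation with no drug effect (400,000 subjects per setting) assumed four independent tests, ULN at the 97.5th percentile, one repeat allowed at screening, and Day 1 as baseline. Totals are per 30 subjects.

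| Within-subject share of variance | Later visits | Normal-to-high results, all tests and visits | Per test-visit cell | Subjects with at least one |
|---|---|---|---|---|
| 10% | 3 | 3.0 | 3.0/(4 x 3) = 0.25 | 2.2 |
| 30% | 4 | 7.2 | 7.2/(4 x 4) = 0.45 | 5.2 |
| 50% | 5 | 11.6 | 11.6/(4 x 5) = 0.58 | 8.2 |

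The baseline definition (SAP 6.1) is redacted. If the qualifying Screening value is baseline, the pooled totals become 4.9, 9.8 and 13.9. Per cell these are 4.9/12 = 0.41, 9.8/16 = 0.61 and 13.9/20 = 0.70. Either way, fewer than one chance count is expected per cell.

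A simpler check takes the chance p of a high result per subject, test and visit as 1%, 2.5% or 5%. Then 30p = 0.3, 0.75 or 1.5, and 1 - (1 - p)^30 = 0.26, 0.53 or 0.79. A lone high count is therefore weak evidence without its size.

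**4. What finer categories could deliver.** The exact 95% upper limit is 11.6% for 0/30 and 21.8% for 0/15; 1/30 has an interval of 0.1% to 17.2%. Finer categories would show magnitude but would not make rates precise.

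**The case against.** The strongest reply is that the shift table is one output among several. SAP 14.2 gives maxima and changes by visit, and lists every chemistry value. With about 30 subjects, a reader can find anyone above any level in the listing. Protocol 13.4.1 has clinically significant abnormalities recorded as adverse events. These are graded by CTCAE v5.0 and tabulated by worst severity under SAP 14.1, with unknown severity counted as severe. Cells by grade and dose group would mostly hold 0 or 1.

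Most of this stands, and it rules out some stronger inferences. A reader might infer that a liver signal could not be told from noise. The documents do not support that, because magnitude appears in three other places. A reader might also take the simulated 3 to 12 chance shifts to mean that a true case would be buried among them. Those totals pool four tests over all visits, while the table separates them; a true case would often be the only count in its cell.

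The reply does not fully close the gap. Maxima do not count or link subjects, and they miss an unscheduled peak when a scheduled value exists. Appendix 1 orders listings by subject, then test, then date, so ALT and bilirubin from one sample sit in separate blocks and must be matched by eye. Under Protocol 11.2.1.1, a laboratory finding becomes an adverse event through investigator judgement, so adverse event grades are not a systematic summary of the values.

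**Conclusion.** The point holds as a gap in tabulation, of low to moderate weight. SAP 14.2 gives every liver value above ULN the same count, plans no count by size of elevation and no same-sample aminotransferase-bilirubin count, and leaves unscheduled peaks out of its by-visit tables when a scheduled value exists. Magnitude can be recovered from maxima, listings and graded adverse events, but not from any one planned table.

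A reader might see exclusion 3 as the fault. It is not. Normal liver tests at entry make a later rise easier to read as on-study change, and the three-level table would be equally coarse without it.

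The conclusion about the tables follows from the readable text and needs none of the assumed figures. The chance counts depend on the assumed variance shares, independence of tests and number of visits. SAP 14.2 itself shows no redaction. However, the Schedule of Assessments, the baseline definition and one criterion in Protocol 12.3 are redacted, and the table shells are in a separate document. Further liver thresholds or flags there cannot be excluded.

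**What to change.** Add one table to SAP 14.2 giving the worst post-baseline AST, ALT, alkaline phosphatase and total bilirubin per subject, from scheduled, unscheduled, repeat and early-termination samples. Classify by CTCAE v5.0 grade, which the protocol already uses for adverse events, or by stated multiples of ULN. Present it by treatment group and overall. Add a row counting subjects whose aminotransferase and total bilirubin are raised in the same sample. The existing shift tables can stay.

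SAP 6.4 already admits all samples to a worst-value summary, so no new data rule is needed. The cost is a paragraph of SAP text and one table from data already collected. The drawback is sparse cells. The counts should be labelled descriptive, given about 30 subjects and no control arm.
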